assessment until the licensed psychologist/physician can arrive. Suicide prevention steps will be taken in the unlikely event that a participant has active suicidal intentions; these procedures include taking the participant to the Northwestern Medicine Emergency Department or notifying emergency services by calling 911.

During the phone-based protocol, the PHQ-9 questions will not be asked and no other questions that address suicidality are present in the phone-based protocol. During the informed consent process, the research coordinator will tell participants that if they appear to be a risk to themselves or others, the coordinator will call 911 to request emergency services. In the unlikely event that emergency services do need to be requested, the research coordinator will ask all participants their current location at the beginning of each call so that information is available for potential emergency service response. If the participant does not appear to be an imminent threat to themselves or others but would like mental health resources, we will email or mail (depending on participant preference) a copy of the mental health resource list to them.

4.5 Study Timeline. We anticipate recruitment of participants to begin March of 2018, preceded by a brief pilot-testing phase to ensure all procedures run smoothly. We aim to recruit 17 participants per month for three years to reach our local (i.e., Northwestern) target of *N* = 612. Each participant will be invited to complete a baseline (i.e., visit 1), three-month (i.e., visit 2), and six-month (i.e., visit 3) follow-up assessment. The first visit will take between 120-150 minutes and the second and third visits will last 60-90 minutes each. Recruitment for the phone-based protocol is anticipated to begin in July of 2020. Phone-based visits are expected to take approximately 60 minutes. We aim to enroll all 612 participants from the in-person protocol for the phone-based protocol. Each participant in the phone-based protocol will be asked to complete a baseline assessment (visit 1), three-month assessment (visit 2), and six-month assessment (visit 3). These 3 time-points are separate from their inperson visits. The final year of the project will be used for data analysis, manuscript writing, and study close-out.

4.6 Types of assessments completed.

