- 4.14Cognitive impaired adults. Participants with severe cognitive impairment will be considered ineligible for this study. The research coordinator will administer a cognition screener (i.e., SPMSQ) that assess for any severe cognitive impairment to determine eligibility for this study. Participants with known mild-to-moderate cognitive impairment may be referred by clinicians to enhance our participant sample for the dementia supplement. Only those deemed capable of providing consent (based on the SPMSQ score) will be considered for the study and their diagnosis of mild-to-moderate cognitive impairment will be noted in the study's REDCap project.

5.0 Multiple sites:

- 5.1 Study sites. This study is being conducted at two sites: Northwestern University and Boston University Medical Center (BUMC). [name] is the PI of the Northwestern site and [name] is the PI of the BUMC site. Northwestern is the grant-holding site with [name] as the contact PI, but both PIs share overall leadership of the study. Both sites will recruit an equal number of participants (N = 608).
- 5.2 Required approvals. Recruitment will proceed at each individual site only when approved by the local IRB.
- 5.3 Site coordination. The sites are in frequency phone and email contact, and there is a weekly teleconference in place for the PIs and research coordinator to aid in consistency of study procedures. An all-team meeting is scheduled for once per month. To ensure that both sites are using the appropriate documents for the study, there is a shared, secure site on Box.com for all study materials (Note: No patient data or PHI is stored on Box, only study materials). Modifications to study protocols will be discussed among the team during the weekly teleconferences. These teleconferences will also be used to discuss problems, interim results, and eventual closure of the study.
- 5.4 Data management and security. The entire study team has been briefed on proper data management and security procedures. This includes the maintenance of data only on secure study trackers, managed via REDCap. Data security will be a weekly agenda item and data security will be routinely audited in terms of physical records (i.e., paper questionnaires and consent forms) as well as study files. Any and all non-compliance with the study protocol or applicable requirements will be reported to the appropriate IRBs in accordance with local policy.

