6.0 Incomplete Disclosure or Deception:

There is no deception or incomplete disclosure as part of this study.

Recruitment:

We plan to recruit no more than 608 participants. They will be recruited through Northwestern Medicine with the assistance of our physician coinvestigator, [name], and Northwestern Medicine Enterprise Data Warehouse (EDW). EDW contains clinical data from NMHC which is mined by a team of data analysts at Feinberg School of Medicine. The study team will work with the data analysts to define a cohort of patients to be recruited. Patients will then be contacted in accordance with NMHC and NU IRB policy including obtaining physician consent and sending an IRB and NMHC approved mailing (e.g., letter or email) before contacting patients either by phone or by email. The study team will screen for eligible participants using Epic, which is the electronic medical record that these clinics use. Via Epic, the research coordinator(s) will identify potential participants within our physician coinvestigator's schedule and request permission to approach their patients to assess eligibility and interest in the study. Participants will also be screened in clinic waiting rooms. Specifically, with approval from physicians and medical staff, research coordinators will approach potential research participants in Northwesternaffiliated clinics (e.g., Erie Family Health Center) and provide them with information about the study. The physician coinvestigators will also alert the coordinators of eligible participants. Interested participants will be invited to provide informed consent, and will then complete all the research measures relevant to the first visit in a private clinic room. Subsequently, they will be scheduled for their second and third visits. If needed, the research team will contact other physicians within General Internal Medicine at Northwestern Medicine for approval to contact their patients.

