Recruitment for the phone-based protocol will be from enrolled participants in the original protocol. We will recruit the entire cohort of 612 participants from the original protocol.

Participants will receive \$40 upon completion of the baseline visit, \$50 after the 3-month visit, and \$60 after the 6-month visit in the form of cash. In addition, they will receive parking passes at each one of their visits to cover the cost of their parking if they parked in a specified Northwestern garage. If needed, taxi or similar transportation (e.g., Lyft) will be arranged for participants, which will be paid for by the research project. Participants will receive up to \$22.50 for transportation costs. Additionally, participants will receive \$25 upon completion of the cognitive screening questions.

After Visit 1, the participant will receive the 1-page Summary Sheet of the research study as a retention material to remind participants of the importance of the research and what to expect next in the study. Additionally, after each visit the participant will receive a "Thank You Card" as a retention material. These "Thank You Cards" will be handwritten by the principal investigator to include the following text, "Thank you for your participation in our study. With your help, we will be able to talk to patients more clearly. We hope this work will help us provide better health care in the future. We couldn't do it without you!"

For the phone-based protocol, participants will receive \$40 upon completion of the baseline visit, \$50 upon completion of the 3-month follow-up, and \$60 upon completion of the 6-month follow-up. Payment will be made in the form of gift cards (either physical gift card mailed to the participant or e-gift card emailed to the participant, depending on participant preference).

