Using a large sample, we will determine the psychometric properties of health questionnaires across levels of health literacy. Testing will be conducted in English and Spanish, across two modes of administration (paper-and-pencil vs. talking touchscreen). Each participant will have three visits (baseline, 3-month, and 6-month follow-up), described below, in order to determine changes in psychometric properties over time. We will use *differential item functioning* (DIF) and other psychometric analyses to identify questionnaire items with varying characteristics across levels of health literacy. Before the COVID-19 pandemic, our original plan was to recruit $N = 1216$ participants for in-person assessments. At the time of this plan our final N is 728 participants who have completed a health literacy assessment; some of these participants are missing data on subsequent questionnaires. In-person recruitment was put on hold during the COVID-19 pandemic; in order to adapt the the pandemic, a subset of participants ($N = 304$) was invited to a phone-based protocol that included data collection about the impact of COVID-19, vaccine confidence, and health-related quality-of-life (PROMIS-29 profile).

- **Develop alternative modes of test administration that can better accommodate people with low health literacy.** National statistics indicate that 14% of adults in the United States have below basic reading skills, and over 75 million Americans have below basic or basic health literacy skills.¹⁴ These data strongly indicate that many individuals seeking health care will have difficulties with written questionnaires, even those that have been carefully developed such as those in the NIH PROMIS. We will test an alternative mode of administration that has been specifically designed to aid people of low health literacy – a computer-assisted “talking” version that uses speech technology that participants can privately access as needed to have items and response options

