PROMIS Profile	To assess health-related quality of life.
PHQ-9	Self-report measure of depression.
Berlin Questionnaire (for sleep)	Self-report measure of sleep quality.
Purpose and Meaning (NIH Toolbox)	Self-report measure of the degree of meaning and purpose a person feels in their life.
RRS	Self-report measure of negative, repetitive thoughts.
PTSD Checklist	Self-report measure of posttraumatic stress disorder symptoms.
*C-SSRS Lifetime	Self-report measure of recent history of suicidal ideation and behavior. (This is not a variable of interest that will be used only to ensure patients' safety).
*C-SSRS Last Contact	Self-report measure of suicidal ideation and behavior since the individual's most recent assessment. (Used only as necessary to ensure patients' safety).
Exit Interview	

are estimated using full-information approaches that use all available data and can accommodate missing responses. We do not foresee a need for an imputation strategy, but if that were to become necessary, we will update this plan accordingly before running any analyses.

Study Design

This is a randomized experiment aimed at determining whether talking touchscreen technology can reduce DIF and provide a better testing experience, relative to paper-based testing. The original study design is shown below in Table 2, although as a result of the COVID-19 pandemic, we were unable to recruit all 1216 participants, but instead collected additional longitudinal data on a subset of participants ($n = 304$)

Table 2: Study Design			
Northwestern		BUMC	

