The literature exploring the relationship between overall vaccine hesitancy (not specific to COVID-19 vaccine) has also found conflicting directional relationships between vaccine hesitancy and educational status. Although some studies have found greater vaccine refusal or hesitancy in lower education groups,^{44, 45} others have not.⁴⁶ The relationship between health literacy and vaccine views is also not clear, with studies finding conflicting results.⁴⁷ Health literacy is a potential modifiable factor for vulnerable populations with uncertain vaccination views. We seek to explore the relationship between COVID-19 vaccine hesitancy and health literacy in a diverse participant sample of $N = 300$, who are a subset of the parent study.

Hypothesis: We hypothesize that health literacy is a mediator of the relationship between race/ethnicity and vaccine confidence, such that race predicts health literacy, which is in turn inversely associated with vaccine confidence. Using mediation analysis, we will determine how much of the effect of race/ethnicity on vaccine confidence is mediated by health literacy (i.e., the indirect effect) while also estimating the direct and total effect. A sample of 300 participants will be included in this baseline analysis exploring the relationship between race/ethnicity, health literacy (measured by Health LiTT⁴⁸ obtained at the baseline of the parent study), and the VCI which was administered at follow-up during a period of COVID-19 vaccine approval and early administration. This hypothesis was formulated before looking at any of the data from the phone-based protocol.

Measures:

Demographic Covariates

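### The vaccine-confidence mediation is fitted in 300 phone participants although its race-to-literacy path is estimable in up to 728, so unexplained selection into the phone subset may bias the indirect effect in either direction

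*SAP*

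**What the plan says.** **Plan for the phone protocol.** Protocol section 4.5 states "We aim to enroll all 612 participants from the in-person protocol for the phone-based protocol", and the Recruitment section repeats it: "We will recruit the entire cohort of 612 participants from the original protocol". Entry also required interest, verbal consent, a reliable phone connection and adequate hearing.

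**What the SAP reports.** Study Objectives says a subset of 304 "was invited to a phone-based protocol that included data collection about the impact of COVID-19, vaccine confidence, and health-related quality-of-life". Study Design says the team "instead collected additional longitudinal data on a subset of participants", again 304. The same number therefore serves as those approached and those with data. Study Objectives gives the final study N as 728 participants with a completed health literacy assessment.

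**The mediation analysis.** The vaccine-confidence addendum, dated 10 March 2021, asks how much of the race/ethnicity effect on vaccine confidence passes through health literacy. It states: "A sample of 300 participants will be included in this baseline analysis". Health LiTT comes from the parent-study baseline, as do race/ethnicity, age, gender and education. Only the Vaccine Confidence Index (VCI) comes from the phone calls. The model is fitted in lavaan with 95% bootstrap intervals for the indirect effect. The addendum names no weighting or missing-data method. Its limitations cover consent to research, urban setting and language, but not selection into the phone subset.

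**Cohort size.** Protocol section 4.5 has "We aim to recruit 17 participants per month for three years to reach our local (i.e., Northwestern) target of" 612, while the Recruitment section says "We plan to recruit no more than 608 participants". Section 5.1 and SAP Table 2 also give 608 per site.

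**The concern.** The indirect effect is the product of the race-to-literacy path and the literacy-to-VCI path. The first needs nothing from the phone calls, yet the plan estimates it only among people who were invited, reached, willing and able to take part by phone. Each of those steps could plausibly depend on literacy, which is the hypothesised mediator. If so, the literacy difference between race groups among phone participants need not equal the difference in the parent cohort, and any distortion carries in proportion into the quantity the addendum sets out to estimate.

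This source of bias is avoidable, because the data for the first path are already held. Restricting to 300 also discards information. The SAP uses full-information estimation for DIF, and an estimator that includes all cases for the rumination model. It gives no reason for doing otherwise here.

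**Working it through.** **1. The plan's own figures.**
- Northwestern accrual: 17 x 36 months = 612.
- SAP Table 2, per site: 2 languages x 2 literacy levels x 2 sexes x 2 modes x 2 orders x 19 = 608; two sites give 1,216.
- 612 - 608 = 4, or 0.7% of 608. Each figure follows from its own inputs. The gap is bookkeeping and plays no part in what follows.
- Share with a literacy score who enter the mediation: 300/728 = 41.2%. Left out: 728 - 300 = 428 (58.8%).
- The SAP gives no precision calculation for this analysis, so there is none to reproduce.

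**2. Possible bias in the race-to-literacy path.** The documents give no selection data, so these inputs are assumed: two race groups; literacy normal with SD 1 within each group; true difference a = -0.80 SD; logistic participation with odds ratio 1.65 per SD of literacy (ln 1.65 = 0.50); participation p of 41.2% unless stated; other covariates ignored.

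Selection raises a group's mean literacy by δ. To first order δ = ln(OR) x (1 - p) = 0.50 x 0.588 = 0.29; numerical integration gives 0.28. The path among participants is a + δ(minority) - δ(majority).

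| Participation | δ minority | δ majority | Path | Error |
|---|---|---|---|---|
| Unrelated to literacy | 0 | 0 | -0.80 | none |
| Same slope, same rate in both groups | 0.28 | 0.28 | -0.80 | none |
| Slope in minority group only | 0.28 | 0 | -0.52 | 35% too small |
| Slope in majority group only | 0 | 0.28 | -1.08 | 35% too large |
| Same slope; minority 30%, majority 55% | 0.33 | 0.21 | -0.68 | 15% too small |
| Same slope; minority 55%, majority 30% | 0.21 | 0.33 | -0.92 | 15% too large |

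Different participation rates by race, with no dependence on literacy, leave the path unbiased. Simulation with a true difference of -0.50 SD, and an odds ratio of 2 or 0.5 in one race group only, gave -0.10 or -0.84 in the selected sample. The full 728 gave about -0.50 throughout. With the literacy-to-VCI slope held fixed, the indirect effect is wrong by the same percentage as the path.

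**3. Precision.**
- Race-to-literacy path: the standard-error ratio is sqrt(300/728) = 0.642, a 36% reduction if all 728 have complete covariates.
- Indirect effect: SE(ab) ≈ sqrt(a² x SE(b)² + b² x SE(a)²). Assume a 40% minority share and unit residual variances. Then SE(b) = 1/sqrt(300) = 0.058 in both analyses, because VCI exists only for the 300. SE(a) = 1/sqrt(0.4 x 0.6 x n) = 0.118 at n = 300 and 0.076 at n = 728.
- With a = -0.80 and b = 0.2, SE(ab) goes from 0.0519 to 0.0486, a 6% reduction. For b = 0.1 and b = 0.4 the formula gives 2% and 16%. Simulation under slightly different assumptions gave 2%, 8% and 17%.

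**The case against.** **The 728 are not a clean benchmark.** Table 2 planned equal numbers with low and adequate literacy, so the parent cohort was itself sampled by quota on the mediator. That can distort a race-to-literacy path. In a simulation with a true value of -0.80, forcing the sample to 50:50 gave -0.88 or -1.07 when 70% or 85% of the source population had low literacy. This stands as a limitation. It applies equally to the 300, who come from the same cohort, so it does not favour the smaller analysis.

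**The denominator is uncertain.** The 612 is Northwestern's target, whereas 728 is the final N of a two-site study, reported in a later version of the SAP than the one that added the vaccine analysis. The SAP does not say which site or sites supplied the 304. Completeness of race/ethnicity and education is not stated, and participants could skip questions. This stands: 728 is an upper bound and 41% is not a firm participation rate. If only one site ran the phone protocol, pooling all 728 would join a two-site first path to a one-site second path unless the model allows for it.

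**The gain for the estimand is modest.** The 36% belongs to one component. The literacy-to-VCI and direct paths still rest on the 300. This also stands.

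**Stronger readings to avoid.** A reader might infer that the 300-person analysis is biased, or biased towards zero. The documents do not show how the 304 were chosen, so neither follows. A reader might also infer a contradiction between the protocol's whole-cohort aim and the SAP's subset. The protocol states an aim in July 2020 and the SAP reports what happened later, so the shortfall needs explaining but is not an inconsistency in itself.

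**Conclusion.** The point holds as a possible and avoidable bias of unknown size and direction. The race-to-literacy path is biased only if phone participation depends on literacy given race and covariates, with a slope or rate that differs between groups. Under the assumed -0.80 SD and odds ratio of 1.65, the range is -0.52 to -1.08, up to 35% either way. These are illustrations, not estimates for this study.

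The precision gain does not depend on whether such bias exists: up to 36% on that path and about 2-17% on the indirect effect, depending on the literacy-to-VCI slope. The analysis is an observational addendum and leaves the randomised mode comparison and the DIF analyses untouched. A change is worth making because the data are in hand and the first path would need a weaker assumption. The mismatches of 612 with 608, and of 304 invited with 304 measured, are minor and do not drive the bias.

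**What to change.** **Analysis.** In the addendum, fit the lavaan mediation by full-information maximum likelihood on all parent participants with Health LiTT and the baseline covariates, with VCI treated as missing outside the phone subset. Add site and language as covariates in both equations. If the phone protocol ran at one site only, limit the model to that site. Keep the bootstrap intervals and report the result beside the 300-person analysis. If the VCI data have already been analysed, label the addition post hoc, as the SAP's own rule requires.

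**Reporting.** State how the subset was chosen and from which site or sites. Give separate counts invited, consented and analysed, in place of 304 in two roles, and account for the step to 300. Compare those included and excluded on race/ethnicity, literacy, education, language and site. Name phone-subset selection, and the literacy quotas of the parent cohort, among the limitations. Reconcile the protocol's 612 with its cap of 608.

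**Cost.** A data merge, one estimation option, two covariates and some text; no new data. The method assumes participation is unrelated to VCI given race, literacy and covariates. It does not improve the literacy-to-VCI or direct paths, which need that assumption in the 300-person analysis as well.
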